The proposed study enrolls approximately 5,000 women in each of four institutions over an average period of 18 months. There are a total of 56 antenatal care units, randomly allocated to provide either the new programme of antenatal care or the programme presently in use. Each group of antenatal care units is expected to be similar in terms of number of clients served, population characteristics (race, ethnicity, religion, socio-economic status, general health conditions), and levels of perinatal outcomes. Women are recruited as they present for antenatal care.

The two programmes of antenatal care will be evaluated in terms of severe maternal and perinatal morbidity. Since maternal mortality is a rare event, it is not feasible to conduct a study to demonstrate an impact of health care on it, and surrogate measures will therefore be used. The sample size calculation is based on the anticipated impact on selected maternal and newborn morbidity indicators. (Assuming that these indicators will have on average an incidence of 100 per 1,000 live births in participating centres, the study is designed to detect a 18% change).

The impact of the two programmes on maternal health will be compared in terms of specific morbidities, their severity, and general measures of morbidity, such as days in hospital and amount of resources consumed during hospital stay.

The impact on neonatal health will be assessed in terms of perinatal and neonatal morbidity, birth weight, gestational age and incidence of specific morbidities, as well as more general measures of neonatal status such as days in special care, including intensive care (where available), condition at discharge and hospital resources consumed. Where there is evidence that the resources required by the programmes differ, the cost effectiveness of programmes of care will be evaluated in different settings.

In addition, the two programmes of antenatal care will be compared in terms of process variables, such as average duration of contact between patient and care provider, average waiting time of patients, cost of antenatal care per pregnancy, patient and provider satisfaction with the services and perceived quality of care in a random sample of the population studied.

The study is coordinated by WHO in collaboration with the local institutions in Argentina, Cuba, Saudi Arabia and Thailand.

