Six thousand seven hundred and sixty five subjects were recruited, 3449 and 3316 subjects in the intervention and control groups respectively. There were 182 missing subjects, a rate of 2.7%, leaving 6583 subjects for data analysis. Among 3379 subjects available for analysis in the intervention group, 3053 (90.3%) subjects were classified to be low risk and eligible for a new basic antenatal care model. The average age was 24.5 years with 18.7% teenage pregnancy. A majority of subjects attended primary school education. There were very few subjects who smoked or used known substance abuse. About 40% of subjects were primigravida. Rh isoimmunization was very rare. There were 182 (2.7%) abortions. More than 90% of the subjects received completed tetanus immunization. Most subjects (95.7%) received iron supplementation. During antenatal care, 144 (2.3%) subjects were referred to a higher level of care, while 180 (2.8%) subjects required antenatal hospital admission. The prevalence of severe anemia (Hb < 90 g/l) were 4.7% and 6.4% in the antenatal and postpartum period respectively. There were 113 (1.8%) subjects with severe urinary tract infection. There were 60 (0.9%) subjects with pregnancy induced hypertension (PIH) but only 26 (0.4%) required treatment. The incidence of maternal morbidity index indicator* was 8.3%. The low birth weight rate was 9.0%. Eight women died, giving a maternal mortality rate of 0.12%. There were 6400 births with 100 (14.5/1000) fetal deaths and 42 (6.7/1000) neonatal deaths. The perinatal mortality rate was 22.2 per 1000 births.

The result of the comparison between the new antenatal care model and the traditional model will be submitted to MotherCare when data from the other 3 sites are available and combined for statistical analysis which is expected to be available in late 1999.

* Maternal morbidity index indicator is defined as the presence of one of the following severe maternal conditions : proteinuric - preclampsia, eclampsia or severe hypertension (> 160/110 mm Hg) during pregnancy or within 24 hours of delivery; postpartum anemia < 90 g/l of hemoglobin and severe urinary tract infection/pyelonephritis, defined as requiring antibiotic treatment or hospitalization.

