proteinuric-preeclampsia or eclampsia (during pregnancy or within 24 h of delivery; post-partum anemia (<90 g/l); severe urinary tract infection/pyelonephritis (requiring antibiotic treatment or hospitalization)

If LNMP not available, use the best "obstetric" estimation; below 10th percentile of international standard

OUTCOMES OF THE ANC RANDOMIZED CONTROLLED TRIAL
(contd.)

C. PROCESS OUTCOMES	Question number in Data Collection Form(s)	Rates
Rate of antenatal hospital admission - total by cause	Hospital admission form	
Rate of elective and emergency cesarean section associated with pregnancy complications (****)	36-46-47 of Summary form	
Days of hospital admission during pregnancy (median)	Hospital admission form	
D. COST OF ANC	Mean (SD) in US\$	
To the health service		
To the patient		
E. SATISFACTION AND PERCEIVED QUALITY OF CARE (only in random sample)		
By the health workers		
By the patient		

**** Excluding intrapartum cesarean section for fetal distress or cephalopelvic disproportion

7. duration of study;
8. loss to follow-up;
9. randomization by cluster;
10. use of randomized pairs or randomized blocks to increase the precision of comparisons;
11. study areas (countries; sites within country; clinics or hospitals within areas).

Changing the specification of any one of the above factors can have a major effect on the estimate of the sample size. Some of these factors have specific relevance in reference to the present protocol.

The major endpoint

Any one of the many endpoints of interest itemized in the protocol can be used to estimate the required size of this study, with the sample size varying by the endpoint chosen. Among these endpoints, there are two primary outcomes of major public health importance which the new programme must demonstrate will not increase: namely, the maternal morbidity index and low birth weight. Thus, the average minimum rate obtained for individual rates from areas to be enrolled in the study (about 10%) will be used to plan the size of the proposed investigation.

Baseline values

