Subject number list forms were used to record names and some information of every subject recruited into the study. Classifying forms were used to classify women only in the intervention hospitals into low and high risk groups. Low risk women received new basic antenatal care scheme. High risk women were managed according to the recommended treatment in that hospital or referred to a higher level of care. Antenatal hospital admission forms were completed for women admitted to the hospital for various conditions before delivery. Summary forms were completed for all women recruited into the study regardless of their pregnancy outcomes.

Principal investigators or coinvestigators or field coordinators visited these 12 hospitals fortnightly during the first 3 months and once a month for the rest of the 12 month recruitment and 6 month follow up period. This was to ensure a good quality recruitment, follow up and data collection procedure.

Responsible persons in each hospital were requested to send all forms (subject number list, classifying forms (in intervention hospitals), antenatal hospital admission and summary forms) monthly to the provincial health office where the field coordinators checked the actual number of forms received with the number indicated in the batch cover form. All forms were transferred from the provincial health office to the data coordinating unit at the Faculty of Medicine, Khon Kaen University. Data were doubly entered using the SPSS/DMS2 program provided by the Special Programme of Research, Development and Research Training in Human Reproduction, The World Health Organization, Geneva, Switzerland. Data were checked by various checking mechanisms. Query sheets were produced and sent to respective hospitals by facsimile. Update of the data was performed when response was obtained from hospitals. Data were transferred monthly to the central coordinating unit in Geneva via electronic mail. Summary forms for maternal deaths, fetal deaths and eclampsia cases had to be faxed to the coordinating unit in Khon Kaen University as soon as possible. These forms were then transferred to the central coordinating unit in Geneva also by fax. Number of these adverse outcomes by arms of the trial were reported periodically to the data safety monitoring committee only.

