5. RESULTS

Since the study in Thailand is a part of the multicenter WHO study the final evaluation of the new antenatal care model requires a combination of subjects from the 4 study sites to reach a targeted sample size. This report presents only descriptive data combining subjects from both the intervention and control groups.

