5.2.3 Antenatal care

About 35.9% and 50.4% of the subjects started their antenatal care in the first and second trimester respectively, Table 22.

Median number of total ANC visits in the intervention and control groups were 4 (range 1-14) and 7 (range 1-20) respectively. In the intervention group, median number of visits to the original clinic, to other clinic and to high risk clinic were 3, 3 and 1 respectively. The corresponding figures in the control group were 5, 4 and 1 respectively, Table 23.

A high rate of completed tetanus immunization (90.5%) was achieved among these subjects. Most subjects (95.7%) had received iron supplementation. There were 144 (2.3%) subjects referred to a higher level of care. The 2 most common indications were uterine height low for gestational age and vaginal bleeding. There were 180 antenatal hospital admissions. The 3 most common indications were vaginal bleeding, preterm labor and urinary tract infection.

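### Table 6 fixes the median for antenatal hospital days without a denominator, and on neither reading does it compare hospital burden between the arms

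*Protocol*

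**What the plan says.** Part C of Table 6 (printed within Protocol section 4.8.1) lists the process outcomes. One is "Days of hospital admission during pregnancy (median"), with the hospital admission form as its source. The row gives a summary statistic but no denominator. Another row of part C is "Rate of antenatal hospital admission - total by cause", so the incidence of admission is a separate outcome.

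The Executive Summary says why days matter. The two programmes are to be compared on general measures of maternal morbidity, "such as days in hospital and amount of resources consumed during hospital stay".

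Two places bear on the denominator:

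- The Khon Kaen implementation section (numbered 4.1.6) says "Antenatal hospital admission forms were completed for women admitted to the hospital for various conditions before delivery". The named source therefore exists only for admitted women.
- Section 4.10.1 bases the principal analyses on clusters as allocated, which points to all women.

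On frequency, the Executive Summary reports that "180 (2.8%) subjects required antenatal hospital admission" in Khon Kaen. Section 5.2.3 gives the same count as "There were 180 antenatal hospital admissions". Section 5 warns that "This report presents only descriptive data combining subjects from both the intervention and control groups".

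**The concern.** Days in hospital are meant to show whether one model of care leads to more hospital use than the other. That calls for a quantity per woman enrolled, because the clinics, and through them all their women, were randomised. A median does not supply it when most women have no admission. Taken over everyone, it is zero unless at least half are admitted. Taken over the admitted, it drops everyone else and depends on who gets admitted.

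The protocol expects the new model to act on that selection. Section 4.4.2 prefers more frequent checks at primary level over hospital referral. Table 2 lists emergency admissions, and referred cases against urgent admissions, among its process indicators. If admission practice differs by arm, the admitted women in the two arms are not comparable groups. A lower median could then mean shorter illness, or only more short admissions.

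At stake is one process measure of hospital use. A reader of the final report could take equal or lower medians as evidence that hospital burden did not rise, when the statistic cannot show that.

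**Working it through.** **1. The document's own rate.** Section 5.2 and Table 17 give 6583 summary forms, of which 23 were not pregnant, 182 were abortions and 24 had moved away.

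- 6583 − 23 − 182 − 24 = 6354, the total in Tables 24 and 25.
- 180 / 6354 = 2.83%, which reproduces the stated 2.8%.
- If 180 counts admissions rather than women, the share of women is this or lower.

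**2. Reading A: all women.** The median is 0 whenever fewer than half the values are above 0.

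- In Khon Kaen (Table 16), a non-zero median needs at least 1690 of 3379 intervention women or 1602 of 3204 control women admitted.
- The arms are pooled in the report. If all 180 fell in the smaller arm, the rate would be 180 / 3204 = 5.6%, against the 50% needed.
- No rate is given for the other three sites. With about 20,000 women in all, a pooled median above 0 would need (10,000 − 180) / (20,000 − 6354) = 9820 / 13,646 = 72% admitted elsewhere.

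On this reading the result is 0 against 0, and it does not depend on the exact rate.

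**3. Reading B: admitted women only.** The document gives no lengths of stay, so this step is an illustration. Assume geometric stays with a mean of 4 days, for which P(stay ≤ k) = 1 − 0.75^k.

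- Base: 280 stays (2.8% of 10,000 women). P(≤ 2) = 0.44 and P(≤ 3) = 0.58, so the median is 3 days. Total days = 280 × 4 = 1120.
- Add 280 one-day stays. One-day stays are now 280 + 0.25 × 280 = 350 of 560, or 62.5%, so the median is 1 day. Total days = 1120 + 280 = 1400.
- Change in total: 1400 / 1120 = 1.25, a rise of 25%.

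**4. Does the admission rate close the gap?** Same scenario, per 10,000 women:

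| | Base | With added stays |
|---|---|---|
| Admission rate | 2.8% | 5.6% |
| Median among admitted (days) | 3 | 1 |
| Rate × median | 0.084 | 0.056 |
| Mean days per woman | 0.112 | 0.140 |

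The rate shows that admissions doubled. Rate and median together do not recover days per woman: their product falls by a third while the true mean rises by a quarter.

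**The case against.** The strongest reply is that the row means length of stay among admitted women. The evidence for that is good. The named form exists only for admitted women. The summary form asks every woman about any antenatal admission (question 27), but Table 6 does not cite it for this row. Table 23 appears to follow the same convention: its ranges all start at 1, and it gives a median of 1 visit to the high-risk clinic in each arm although section 5.2.3 reports only 2.3% of women referred to higher care. Over all women that median would presumably be 0.

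A reader might therefore be tempted to say that the outcome is zero in both arms by construction and can show no difference. The document does not support that. It is true only on the all-women reading, which the protocol does not fix and which is the less likely one. Among admitted women the median is above 0 if a form implies a stay of at least one day, and it can differ. With 90 admitted women per arm and assumed geometric stays averaging 3 and 5 days, the sample medians average about 2.1 and 3.6. Nor can the Khon Kaen 2.8% be read as the trial's admission rate: it is one site's result with arms pooled.

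Other parts of the reply also stand. Incidence plus length of stay is an ordinary two-part description, and Table 6 already lists the incidence. Cost has its own rows, summarised by mean and SD, and nothing says that the median feeds them. The outcome is in none of the dummy tables I to IX.

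The reply does not make the median a comparison of burden. Length of stay among the admitted is legitimate description, but it contrasts groups formed after randomisation. A denominator may be left to an analysis plan, but the protocol has already fixed the statistic, and neither denominator makes it measure days per woman.

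**Conclusion.** The point holds as a minor one. Table 6 fixes a median with no denominator, and neither denominator yields a valid between-arm comparison of hospital burden. Over all women it is 0 in both arms at any admission rate below 50%, which needs no assumption about the other sites beyond that bound. Over admitted women, the likelier reading, it is informative about those women but selected after randomisation, and it can move against total days: median from about 3 to 1, total up about 25%. That size rests on an assumed geometric stay with a mean of 4 days. The direction needs only that the added admissions be short. The admission rate already listed reduces the risk of misreading without removing it.

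No primary outcome or sample size calculation uses this row.

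**What to change.** In Table 6, make the between-arm comparison mean antenatal hospital days per woman enrolled, counting women without an admission as zero. Base the inference on clusters, by clinic-level means or a cluster bootstrap, within the stratified design. Report it beside the admission rate already listed. Keep the median stay among admitted women as description only, and label its denominator.

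The cost is one line in Table 6 and a small change in the analysis. No new data are needed if the hospital admission form records length of stay, as its citation for this row implies; question 27 of the summary form identifies the zeros. The price is that a mean of such skewed data is sensitive to a few long stays and will be less stable than a median.

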4.8.2 Sample size

(The determination of sample size included here has been prepared with the support of [name] PhD.)

The determination of sample size presented here uses a stratified cluster randomization design to compare the intervention with the standard treatment.

The outcome dichotomous variable is low birthweight: there are four or five strata or countries, the clusters being the clinics or hospitals within the country. By fixing the time period for recruiting, the investigator can control the cluster size.

The question addressed is the determination of the total number of individuals needed and the number of clusters in each stratum, to achieve a certain power and confiability in comparing the two rates. Formula 2 of Donner (1992) will be used to obtain an answer.

The calculations are made in two steps, the first step being the estimation of the intra-cluster correlation, and the second step is the implementation of Donner's Formula 2 (Donner, 1992).

Estimation of the intra-cluster correlation

Estimation of the intra-class correlation was done using standard formulas applied to dichotomous data as described in Fleiss (1981), Formula 13.42, using a data set from four clinics and four hospitals in Argentina with the dichotomized variable low birth weight. The

estimation was made for the future study assuming cluster sizes of 300, 450 and 600 (md), using the components of variance estimates from the data set to compute the Between and Within Mean Squares (BMS and WMS respectively) needed in Formula 13.42. The estimates, done separately for hospitals and clinics, were respectively .00005 and .00008, which average .00065.

Implementation of Donner (1992)'s Formula 2

The stratum-specific success rates P_c were taken to be equally spaced from .07 to .13 (four strata, $i=1, \dots, 4$), or from .06 to .14 (five strata, $i=1, \dots, 5$). Calculations were made also for five strata because there is the possibility to include a fifth country in the study.

Two values were assumed for the odds ratio (OR), namely 1.16 and 1.20, and the stratum-specific success rates P , $i=1, \dots, 4$ or 5 were derived from the P_c 's and the OR's. Three values were taken for the cluster sizes, namely 300, 450 and 600. A constant number of clusters in each stratum was assumed, so that

$$t_i = \frac{m_i}{4} = 1 \quad \text{or} \quad t_i = \frac{m_i}{5} = 1$$

$$\sum_{i=1} m_i \qquad \sum_{i=1} m_i$$

Using the above values and the value for the intra-class correlation coefficient estimated from the Argentinian data set, as well as other values close to it, Formula 2 of Donner's was implemented for a two-sided test, a level of significance of .05 ($z_\alpha = 1.96$) and a power of 80% ($z_\beta = .842$).

The results are shown in Tables 7a, 7b and 7c. Please note that Table 7c presents sample size calculations for $\beta = 0.10$ or a power of 90%. This is done to evaluate the effect on the sample size of an approach to reduce the risk of false negative results. For example, take the usual objective of showing that the new model of ANC is more effective than the traditional model:

		REALITY	
		Equivalent	Not equivalent
DECISION	Equivalent		β
	Not equivalent	α	

β = Probability of concluding that the two methods are equivalent, when in fact they are not (say = 0.10).

Suppose the true O.R. = 1.18; we observe, say OR = 1.10. If SE (LnOR) is 0.05,

$$x^2 = \frac{\text{LnOR}^2}{\text{SE}^2 (\text{LnOR})} = 3.6 < 3.84$$

If we conclude that “methods are equivalent”, we are making a mistake. We will do so whenever we observe $\text{OR} < 1.11$. We want then that the probability of making this mistake to be $\beta < 0.10$. The implications of this requirement on the sample size are presented in Table 7c.

From these tables we can see that for $\alpha = 0.05$ and $\beta = 0.20$ for an OR 1.18 and four study sites, a total sample size of approximately 16,000 women is needed, distributed in ten clinics of 450 pregnancies per study site (Table 7a). If we have five study sites, eight clinics per site will be needed (Table 7b). However, we would like to have a power of 90% ($\beta = 0.10$); we will need twelve clinics of 450 pregnancies in each of the four study sites for a

Table 7(a): Total number of individuals (N) and number of clusters per stratum per group (n), for P_c ranging from .07 to .13 in four strata $\alpha = 0.05; \beta = 0.20$

ρ	OR	Size of temporal block m_1					
		300		450		600	
		N	n	N	n	N	n
0	1.16*	15040	7	15040	5	15040	4
	1.18**	12016	5	12016	4	12016	3
	1.20	9841	5	9841	3	9841	2
.00065	1.16	17963	8	19430	6	20896	5
	1.18	14352	6	15523	5	16695	4
	1.20	11753	5	12713	4	13672	3
.001	1.16	19537	9	21793	6	24049	5
	1.18	15609	7	17411	5	19214	4
	1.20	12783	6	14259	4	15735	4
.002	1.16	24034	10	28546	8	33058	7
	1.18	19202	8	22807	7	26411	6
	1.20	15725	7	18677	6	21630	5

N is value obtained from formula (2) of Donner (1992).

Note: $300 \times 4 \times 2 \times n \approx N$. This is only approximate because values of n have been rounded up to give integer numbers.

ρ = intracluster correlation coefficient; shaded ρ was obtained using data from hospitals & clinics from one of the study sites (Villar et al, 1994)

O.R. - odds ratio

* O.R. = 1.16 corresponds to $P_c = 0.10$ and $P_i = 0.114$

** O.R. = 1.18 corresponds to $P_c = 0.10$ and $P_i = 0.116$

Table 7(b): Total number of individuals (N) and number of clusters per stratum per group (n), for P_c ranging from .06 to .14 in five strata $\alpha = 0.05$; $\beta = 0.20$

ρ	OR	Size of temporal block m_1					
		300		450		600	
		N	n	N	n	N	n
0	1.16*	15097	5	15097	4	15097	3
	1.18**	12062	4	12062	3	12062	2
	1.20	9879	4	9879	3	9879	2
.00065	1.16	18031	6	19503	5	20975	4
	1.18	14406	5	15582	4	16758	3
	1.20	11799	4	12762	3	13725	3
.001	1.16	19611	7	21875	5	24140	4
	1.18	15669	6	17478	4	19287	4
	1.20	12832	5	14314	4	15796	3
.002	1.16	24125	8	28654	7	33183	6
	1.18	19275	7	22894	5	26512	5
	1.20	15786	6	18750	5	21713	4

N is value obtained from formula (2) of Donner (1992).

Note: $300 \times 5 \times 2 \times n \cong N$. This is only approximate because values of n have been rounded up to give integer numbers.

ρ = intracluster correlation coefficient; shaded ρ was obtained using data from hospitals and clinics from one of the study sites (Villar et al, 1994).

O.R. - odds ratio

* O.R. = 1.16 corresponds to $P_c = 0.10$ and $P_1 = 0.114$

** O.R. = 1.18 corresponds to $P_c = 0.10$ and $P_1 = 0.116$

Table 7(c): Total number of individuals (N) and number of clusters per stratum per group (n), for P_{ic} ranging from .07 to .13 in four strata $\alpha = 0.05$ (2-sided) and $\beta = .10$

ρ	OR	Size of temporal block m_1					
		300		450		600	
		N	n	N	n	N	n
0	1.16*	20134	9	20134	6	20134	5
	1.18**	16085	7	16085	5	16085	4
	1.20	13173	6	13173	4	13173	3
.00065	1.16	24046	10	26009	8	27972	6
	1.18	19211	8	20780	6	22348	5
	1.20	15733	7	17017	5	18302	4
.001	1.16	26153	11	29173	9	32193	7
	1.18	20895	9	23307	7	25720	6
	1.20	17111	8	19087	6	21063	5
.002	1.16	32173	14	38213	11	44253	10
	1.18	25704	11	30530	9	35355	8
	1.20	21050	9	25002	7	28953	6

N is value obtained from formula (2) of Donner (1992).

Note: $300 \times 5 \times 2 \times n \approx N$. This is only approximate because values of n have been rounded up to give integer numbers.

ρ = intracluster correlation coefficient; shaded ρ was obtained using data from hospitals and clinics from one of the study sites (Villar et al, 1994).

O.R. - odds ratio

* O.R. = 1.16 corresponds to $P_c = 0.10$ and $P_t = 0.114$

** O.R. = 1.18 corresponds to $P_c = 0.10$ and $P_t = 0.116$

total 21,000 patients (Table 7c). Thus, the study will aim at recruiting at least four study sites which can provide twelve antenatal care clinics of 450 pregnancies during no more than 18 months of patient enrollment.

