The population attending the clinics in each country should be similar with regard to sociodemographic factors, and have study-relevant mortality and morbidity rates in the same order of magnitude. An antenatal care programme following traditional standards delivered through the public sector should be already available to pregnant women. Furthermore, all participants should plan to deliver in hospitals, not least for practical recording purposes. To obtain a reliable answer within a reasonable period of time, there will be several antenatal care clinics (clusters) for comparison, stratified by study site and cluster size. Each clinic or cluster will be expected to manage between 450 and 500 antenatal care patients during the study period. However, as it is more important the number of clusters than the size of them it is possible that for logistic reasons smaller antenatal care clusters could be accepted (about 300 antenatal care patients per cluster).

Each site considered for the study should be able to:

1. produce reliable data on the primary maternal and newborn outcomes in the city or region.
2. Provide written evidence that the new programme will be acceptable to local authorities and physicians.
3. Recruit between 10 and 12 antenatal clinics from the public sector (see criteria for clinic selection) in a geographically identified region.
4. Have a common formal system of perinatal data collection and maternal cards already in place.
5. Have an effective system for referral of high-risk women from the clinics to a tertiary level hospital.

6. Have a regional epidemiological research unit with field research experience; previous participation of this unit in multicentre studies is required. Computer facilities at the research unit-hospital or university-should be available to the study group.
7. Country should allow data (multicentre trial) to be sent to the central analysis centre (Geneva) and to be pooled with those from the other centres.

The criteria for each antenatal care clinic to be included for randomization is as follows :

1. Each antenatal care clinic (the randomization unit) to be included should be able to provide between 300 and 500 new patients in a period not longer than 18 months.
2. Intervention and control clinics will be in the same geographical area.
3. "Same geographical area" relates to same city or district; the ideal situation will be clinics serving different neighbourhoods of a city or areas of a rural province.

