Uncomplicated deliveries are attended and conducted by nurses. Complicated deliveries are managed by medical officers or referred to higher level of care as appropriate. Facilities for cesarean section are available in all 3 sixty-bed and 6 thirty-bed community hospitals and some ten-bed hospitals.

Nurses from the community hospitals and midwives from the health centres make a home visit for postpartum women in their respective areas. Health education and management of postpartum complications are provided as appropriate.

The name of the clinics (clusters) and their expected number of new antenatal care patients per year and low birth weight rate is shown in Table 1.

Table 1 : Antenatal Care Clinics (Clusters) included in the study

Stratum	Clinic Number	No. of new Antenatal Care patients/year	LBW rate
Thailand (large)			
Chumpae	01	1330	8.0
Kranuan	02	1025	10.0
Thailand (medium)			
Banphai	03	669	5.6
Phol	04	469	9.1
Manjakiri	05	466	11.3
Nongsonghong	06	464	9.4
Nongrua	07	451	5.6
Phuwiang	08	445	5.6
Thailand (small)			
Srichompoo	09	293	6.7
Nampong	10	268	7.9
Khaosuankwang	11	250	8.0
Waeng Noi	12	204	4.4

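### Section 4.8.2 sizes the trial as if all clinics were equal, but the protocol's own clinic sizes vary widely, so the design effect and the N for 90% power are modestly understated

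*Protocol*

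**What the plan says.** Section 4.8.2 of the Protocol works in two steps: estimate the intracluster correlation, then apply a published sample-size formula for stratified cluster designs. It states that "Formula 2 of Donner's was implemented for a two-sided test, a level of significance of .05". Tables 7a to 7c give results for clinic sizes of 300, 450 and 600, each taken as common to all clinics, with no term for variation in size. On the reason size can be treated as a design constant, the section says "By fixing the time period for recruiting, the investigator can control the cluster size". The adopted design is twelve clinics of 450 in each of four sites, quoted as 21,000 women and resting on the 20,780 of Table 7c.

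Other parts of the Protocol bear on clinic size:
- Section 4.2.2 says each clinic "should be able to provide between 300 and 500 new patients in a period not longer than 18 months".
- Section 4.3, Table 1, headed "Antenatal Care Clinics (Clusters) included in the study", lists twelve Khon Kaen clinics expecting 204 to 1,330 new patients per year.
- Sections 4.2 and 4.6 stratify the randomization by clinic size within site.
- The section on implementation in Khon Kaen (numbered 4.1.6) describes one common recruitment year in all twelve hospitals, taking every attender. Table 16 reports 219 to 1,064 women recruited per clinic.
- The Executive Summary plans about 5,000 women in each of four institutions and 56 clinics in total.

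**The concern.** A recruiting period common to all clinics sets their average size but leaves the ratios between them unchanged. A clinic with six times the attendance contributes six times the women. Equal clinics would need clinic-specific periods or a cap, and Khon Kaen had neither.

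When clinics differ in size and women are weighted equally, as in the cluster-adapted Mantel-Haenszel test of section 4.10.1, the variance inflation depends on Σm²/Σm. That quantity always exceeds the mean size when sizes vary, so the error runs in one direction: the design effect is too small and the stated N too favourable. Stratifying by size balances the arms. It does not remove the penalty, because large clinics still carry most of the women.

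The stake is the stated 90% power. Section 4.8.2 chose it over 80% to limit the risk of wrongly declaring the two models equivalent.

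**Working it through.** **Inputs (section 4.8.2 unless noted).** Two-sided α = .05. Power: "However, we would like to have a power of 90"%. Effect: "O.R. = 1.18 corresponds to" 0.10 against 0.116. Control rates "were taken to be equally spaced from .07 to .13 (four strata"). ρ = .00065, m = 450. Table 7c gives N₀ = 16,085 at ρ = 0. Clinic sizes are from Tables 1 and 16.

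**1. The plan's own figure.** Equal-size design effect: DE = 1 + (m − 1)ρ = 1 + 449 × .00065 = 1.292. N = 16,085 × 1.29185 = 20,779, against the printed 20,780. Rebuilding the stratified formula from the four control rates and the odds ratio gives 20,773. The OR 1.18 cells of Tables 7a and 7c agree within 0.1%. This confirms that the tables use equal clinics.

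**2. Spread of clinic sizes.**
- Table 1: Σm = 6,334, mean 527.8, Σm² = 4,582,714, Σm²/Σm = 723.5. Then 1 + CV² = 723.5/527.8 = 1.371, so CV = 0.61.
- Table 16: Σm = 6,765, mean 563.8, Σm² = 4,493,089, Σm²/Σm = 664.2. Then 1 + CV² = 664.2/563.8 = 1.178, so CV = 0.42.

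**3. Design effect and N with unequal clinics, mean 450.** DE = 1 + [(1 + CV²)m − 1]ρ.
- CV 0.42: 1 + (530.2 − 1) × .00065 = 1.344; N = 16,085 × 1.344 ≈ 21,600.
- CV 0.61: 1 + (616.8 − 1) × .00065 = 1.400; N = 16,085 × 1.4003 ≈ 22,500, which is 8.4% above 20,780.

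**4. Power.** Power = Φ{(1.960 + 1.282)√[N/(16,085 × DE)] − 1.960}. For the 48 × 450 = 21,600 design with CV 0.61: √(21,600/22,524) = 0.979; 3.242 × 0.979 − 1.960 = 1.214; Φ = 88.8%.

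| Design, ρ = .00065 | Equal | CV 0.42 in all sites | CV 0.61 in all sites |
|---|---|---|---|
| 21,600 in 48 clinics | 91.1% | 90.0% | 88.8% |
| 20,000 in 48 clinics | 89.4% | 88.3% | 87.0% |
| 20,000 in 56 clinics | 90.3% | 89.3% | 88.3% |

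**5. Only Khon Kaen unequal, 36 other clinics equal.**
- Table 1 shape scaled to mean 450, others 450: Σm²/Σm = 491.7, DE 1.319, N for 90% ≈ 21,200, power at 21,600 = 90.5%.
- Table 1 sizes as printed, others sharing the remaining 15,266 (424 each): Σm²/Σm = 511.9, DE 1.332, N ≈ 21,400, power at 21,600 = 90.2%.
- Table 1 sizes as printed, others 450 (total 22,534): Σm²/Σm = 526.9, DE 1.342, N ≈ 21,600, power 91.2%.

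**6. Larger correlations tabulated in the Protocol, 21,600 in 48 clinics.** Equal against CV 0.61 in all sites: 87.7% against 84.0% at ρ = .001; 77.8% against 71.0% at ρ = .002.

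**The case against.** The strongest reply is that the effect is too small to matter. Rounding up to 48 clinics of 450 already buys slack: 91.1% with equal clinics. Even with the Table 1 spread in every site, power is 88.8%, about one point below target, and weighting clinics optimally would bring it to 89.5%. With the recruited Khon Kaen spread everywhere it is 90.0%. The Protocol gives no clinic sizes for the other three sites, so extending Khon Kaen to them is an assumption. If only Khon Kaen varies, 90% is met. All of this stands, and it rules out any claim that the planned power is lost.

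A reader might also put the Khon Kaen mean of 528 into the formula, hold N at 20,780, and conclude that power falls to 86% or that 23,600 women are needed. The documents do not support that. It cuts the trial to 20,780/528 ≈ 39 clinics, while the plan has 48 or more. Forty-eight clinics with the Table 1 sizes repeated in every site hold 25,336 women and give 91.9%.

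Nor does "A constant number of clusters in each stratum was assumed" help the argument: that sentence is about the number of clusters, not their size.

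The clinic criterion is only partly at odds with Table 1. It covers up to 18 months, over which the smallest clinic (204 a year) would reach 306, and it can be read as a capacity requirement. The three clinics above 500 within a single year (1,330, 1,025 and 669) are what need explaining.

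Finally, the correlation matters more than the size spread: with equal clinics, moving ρ from .00065 to .002 alone takes the 21,600 design from 91.1% to 77.8%. That is true, but it is a separate question and does not make the equal-size formula right.

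**Conclusion.** The point holds in a modest form. The equal-clinic design effect contradicts Table 1, Table 16 and the uncapped common recruitment year in Khon Kaen, and the sentence about controlling cluster size is wrong for a common recruiting period. At ρ = .00065 and mean 450, the design effect should be 1.34 to 1.40, against 1.29. Allowing for the spread raises N for 90% by about 4% to 8% if all sites vary like Khon Kaen, and by about 2% to 4% if only Khon Kaen varies as in Table 1.

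Power of the 21,600 design drops by about 1 to 2 points. The margin is thinner at the roughly 20,000 women of the Executive Summary, where the Table 1 spread in all sites gives 87.0% in 48 clinics or 88.3% in 56. It is worse at the larger correlations the Protocol tabulates.

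These figures assume that women are weighted equally in the analysis, that ρ is the same in clinics of every size, and, for the upper end, that the three unlisted sites are as unequal as Khon Kaen.

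**What to change.** In section 4.8.2:
- Replace 1 + (m − 1)ρ by 1 + [(1 + CV²)m − 1]ρ, with CV and mean taken from the expected clinic sizes at each site.
- Restate N and power for the number of clinics actually planned (48 or 56) and for the planned total (20,000, 21,000 or 21,600), and show the result at ρ = .001 and .002 as well.
- Remove the sentence on controlling cluster size, or limit it to average size.

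In section 4.2.2, reconcile the 300–500 criterion with the Table 1 clinics above 500, for example by saying whether it is a minimum capacity or a range.

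The cost is one recalculation and a few lines of text. The stated power falls by a point or two, and no extra patients are needed.
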